## 1.4 Risk-Benefit Assessment

Enzalutamide is a novel small molecule designed to have an increased affinity for the AR and more effective suppression of the androgen pathway in the setting of androgen overexpression [Tran et al, 2009]. Enzalutamide has a higher binding affinity to the AR (8 times greater), has

- CONFIDENTIAL -

no agonist activity and has demonstrated superior AR downstream effects in the setting of androgen overexpression compared to bicalutamide in preclinical studies.

The efficacy of enzalutamide in subjects with metastatic prostate cancer who progressed on ADT has been demonstrated in 5 randomized controlled phase 3 studies including study PREVAIL in asymptomatic or mildly symptomatic subjects and AFFIRM in subjects with more advanced disease who previously received docetaxel. Regardless of study arm, subjects remained on ADT in both PREVAIL and AFFIRM studies. These studies demonstrated a statistically significant advantage of enzalutamide treatment over placebo across multiple clinically relevant endpoints such as OS, rPFS, time to first skeletal-related event, time to PSA progression, PSA response rate, best overall soft tissue response, and QoL as measured by the Functional Assessment of Cancer Therapy-Prostate (FACT-P). Study PREVAIL showed a significant benefit of enzalutamide in time to initiation of cytotoxic chemotherapy.

Study PREVAIL (chemotherapy naïve mCRPC subjects) was stopped after a planned interim analysis (conducted when 540 deaths had been reported) and showed a benefit of the active treatment. The rate of rPFS at 12 months was 65% among subjects treated with enzalutamide, as compared with 14% among subjects receiving placebo (81% risk reduction; HR in the enzalutamide group, 0.19; 95% CI, 0.15 to 0.23;  $P < 0.001$ ). A total of 626 subjects (72%) in the enzalutamide group, as compared with 532 subjects (63%) in the placebo group, were alive at the data cutoff date (29% reduction in the risk of death; HR, 0.71; 95% CI, 0.60 to 0.84;  $P < 0.0001$ ). The benefit of enzalutamide was shown with respect to all secondary endpoints, including the time until the initiation of cytotoxic chemotherapy (HR, 0.35), the time until the first skeletal-related event (HR, 0.72), a complete or partial soft tissue response (59% versus 5%), the time until PSA progression (HR, 0.17), and a rate of decline of at least 50% in PSA (78% versus 3%) ( $P < 0.001$  for all comparisons).

In PREVAIL, at 5 years a statistically significant increase in OS time was observed in patients treated with enzalutamide compared to placebo (HR = 0.835, 95% CI: 0.751, 0.928;  $P = 0.0008$ ; median: 35.5 and 31.4 months, respectively). The 5-year OS rate was 26% for the enzalutamide arm compared to 21% for the placebo arm, despite that 28% of patients on placebo crossed over to enzalutamide and there was a high rate of subsequent antineoplastic therapy use for prostate cancer. The significant treatment effect seen in earlier analyses was maintained.

Study AFFIRM (postchemotherapy mCRPC subjects) demonstrated that enzalutamide treatment decreased the risk of death by 37% (HR, 0.631 [0.529, 0.752];  $P < 0.0001$ ) compared with placebo treatment. The median survival was 18.4 months in the enzalutamide arm and 13.6 months in the placebo arm (difference = 4.8 months). The statistically significant and clinically meaningful benefit of enzalutamide treatment as measured by OS was seen in all prespecified subject subgroups and observed despite 42.0% of enzalutamide-treated and 61.4% of placebo-treated subjects receiving subsequent therapies to treat prostate cancer, including abiraterone (20.9% versus 24.3%) and cabazitaxel (9.8% versus 13.8%), both shown to improve OS following docetaxel treatment. Enzalutamide

- CONFIDENTIAL -

treatment also resulted in significant improvements over placebo treatment in all key secondary efficacy endpoints.

In a phase 3, randomized, placebo-controlled study (PROSPER) in patients with nonmetastatic CRPC at high risk of disease progression, treatment with enzalutamide has demonstrated a consistent and clinically meaningful improvement in the primary metastasis-free survival (MFS) endpoint, as well as a delay in the time to onset of new antineoplastic therapies, including cytotoxic chemotherapy. The final analysis of OS (based on a data cutoff date of 15 Oct 2019) showed a statistically significant and clinically meaningful improvement in survival favoring enzalutamide and a 26.6% reduction in the risk of death (HR = 0.734, 95% CI: 0.608, 0.885; P = 0.0011). The efficacy observed with enzalutamide in PROSPER represents a clinically meaningful benefit to patients with nonmetastatic CRPC. Overall, enzalutamide has consistently and robustly demonstrated substantial clinical benefits to patients across the CRPC disease continuum.

In addition, in a phase 2, open-label, single-arm study (9785-CL-0321) in patients with hormone-naïve prostate cancer, 92.5% (62 of 67) of patients had a ≥ 80% decline in PSA from baseline at week 25. Of the 54 patients who were on treatment for 1 year (week 49), 100% had a ≥ 80% decline in PSA from baseline. Of the 26 evaluable patients with metastatic disease at study entry, the best overall response by 2 years (week 97) was 13 (50.0%) patients with CR, 4 (15.4%) patients with PR, 3 (11.5%) patients with non-CR/non-progressive disease (PD), 2 (7.7%) patients with stable disease, 3 (11.5%) patients with PD and 1 (3.8%) patient was not evaluated. At week 97 (2 years of treatment), 45 of 67 (67.2%) patients had a PSA response ≥ 80%; All 45 (100%) patients who were on treatment for 2 years had a ≥ 80% decline in PSA from baseline.

Lastly, the primary efficacy analysis in ARCHES demonstrated a statistically significant, robust and substantial improvement in radiographic progression-free survival together with clinically meaningful improvements in the key secondary endpoints of time to PSA progression, time to start of a new antineoplastic therapy, PSA undetectable rate and objective response rate and a trend in OS (observed at the time of interim analysis) in favor of enzalutamide plus ADT versus placebo plus ADT treatment. For the secondary endpoints, the ARCHES study demonstrated that enzalutamide prolonged the time to the first symptomatic skeletal event and time to castration-resistance. Assessments of patient-reported outcomes data showed that patients receiving enzalutamide plus ADT in ARCHES had a high baseline level of quality of life, which was maintained over time.

Based on the safety information collected to date in clinical trials and in commercial use, the safety profile experienced by patients remains consistent with the approved product label as well as events that can be seen in patients with prostate cancer. The safety profile in mHSPC patients in this study is expected to be consistent with the established safety profile for enzalutamide. To date, the important identified risks associated with enzalutamide are ischemic heart disease, fall, fracture and seizure.

- CONFIDENTIAL -

While serious adverse events (SAEs) such as seizure have occurred in patients receiving treatment with enzalutamide, these events have been rare. To mitigate the risk of seizure, subjects with a history of seizure or any condition that may predispose to seizure (e.g., prior cortical stroke or significant brain trauma, brain arteriovenous malformation) are excluded from the trial. Study drug discontinuation is required for subjects experiencing either seizure or PRES. In addition to these patient exclusion and discontinuation requirements, the study design includes safety labs, scans and guidance related to concomitant medications to minimize the risks associated with enzalutamide and ensure timely intervention if needed.

Based on the information known about the drug and the efficacy results that have been consistently demonstrated in both PREVAIL and AFFIRM, the risk-benefit assessment supports the investigation of enzalutamide plus ADT in men with mHSPC who are hormone sensitive. Medical monitor will be responsible for reviewing the unblinded data from the trial to ensure the safety of the subjects.

The totality of the efficacy and safety data demonstrate a favorable benefit-risk balance for the use of enzalutamide in men with mCRPC and for the continued investigation of enzalutamide in men with earlier stage prostate cancer.

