#### **4.4 Blinding**

##### **4.4.1 Blinding Method**

This is a double-blind study. Subjects will be randomized to receive enzalutamide or placebo in a double-blind fashion such that neither the investigator, sponsor's study management team, clinical staff, nor the subject will know which agent is being administered. The randomization number will be assigned based on information obtained from the Interactive Response Technology (IRT).

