##### **4.4.3 Retention of the Assignment Schedule and Procedures for Treatment Code Breaking**

The randomization list and study medication blind will be maintained by the IRT system.

Unblinding of the study treatment assignment may be performed if the subject discontinues from the study treatment with confirmed radiographic disease progression and in the judgement of the investigator this information is necessary to determine the next course of therapy. Prior to unblinding in this scenario, the investigator must contact the Astellas Medical Monitor.

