##### **4.4.4 Breaking the Treatment Code for Emergency**

The treatment code for each randomized subject will be provided by the IRT in the event of a medical emergency requiring knowledge of the treatment assigned to the subject. If possible, the Astellas Medical Monitor should be contacted prior to unblinding. The time, date, subject number and reason for obtaining any of these codes, and therefore breaking the blind, must be

- CONFIDENTIAL -

documented in the study file. They must only be requested by the investigator or other persons designated as subinvestigators. No subjects or other study personnel will be made aware of the treatment given to any subject unless a medical emergency necessitates such disclosure.

Any unblinding by the investigational staff must be reported immediately to the sponsor and must include an explanation of why the study medication was unblinded.

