#### **4.4.5 Breaking the Treatment Code by the Sponsor**

The sponsor may break the treatment code for subjects who experience a suspected unexpected serious adverse reaction (SUSAR), in order to determine if the individual case or a group of cases requires expedited regulatory reporting. Individual Emergency Codes will be provided to the limited staff that is responsible to break the codes for all SUSAR cases for reporting purposes.

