##### **5.1.2 Increase or Reduction in Dose of the Study Drug(s)**

During the study, subjects who experience a National Cancer Institute (NCI)-Common Terminology Criteria for Adverse Events (CTCAE) guidelines (version 4.03) grade 3 or higher AE (except liver function test [LFT] AE) toxicity that is attributed to the study drug and cannot be ameliorated by the use of adequate medical intervention and/or dose reduction may interrupt

- CONFIDENTIAL -

study drug treatment for 1 week or until the toxicity grade improves to grade 2 or lower in severity. Study drug may be restarted at the original dose (160 mg/day) or a reduced dose (120 mg or 80 mg/day). If restarted at a lower dose or if interrupted for > 2 weeks, the Medical Monitor must be consulted. After dose reduction, based on subject tolerance, study drug may be increased to a maximum dose of 160 mg/day per investigator discretion.

Enzalutamide must be interrupted during the evaluation of symptoms suspicious of PRES (headache, lethargy, confusion, blindness and other visual and neurological disturbances, with or without associated hypertension).

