- Causal relationship to the study drug (including reason), and
- The drug or blinded regimen provided (if any)

The sponsor or sponsor's designee will medically evaluate the SAE and determine if the report meets the requirements for expedited reporting based on seriousness, causality, and expectedness of the events (e.g. Suspected Unexpected Serious Adverse Reaction (SUSAR) reporting) according to current local/regional regulatory requirements in participating countries. The sponsor or sponsor's designee will submit expedited safety reports (e.g., IND Safety Reports, SUSAR, CIOMS-I) to Competent Authorities (CA) and concerned Ethics Committee (cEC) per current local regulations, and will inform the investigators of such regulatory reports as required. Investigators must submit safety reports as required by their Institutional Review Board (IRB)/local Independent Ethics Committee (IEC) within timelines set by regional regulations (cFDA) where required. Documentation of the submission to and receipt by the IRB/local IEC of expedited safety reports should be retained by the site.

The sponsor will notify all investigators responsible for ongoing clinical studies with the study drug of all SUSARs which may require submission per local requirements to the IRB/local IEC. The investigators should provide written documentation of IRB/local IEC notification for each report to the sponsor.

The investigator may contact the sponsor's Medical Monitor/Study Physician for any other problem related to the safety, welfare or rights of the subject.

- CONFIDENTIAL -

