1 INTRODUCTION

[figure not shown]
This Statistical Analysis Plan (SAP) contains a more technical and detailed elaboration of the principal features of the analysis described in the protocol, and includes detailed procedures for executing the statistical analysis of the primary and secondary endpoints and other data.

The SAP is finalized and signed prior to database hard lock to ensure lack of bias. If needed, revisions to the approved SAP may be made prior to database hard lock. Revisions will be version controlled.

Any changes from the analyses planned in the SAP will be justified in the Clinical Study Report.

Prior to database hard lock, a final blinded review of data and TLFs meeting will be held to allow a review of the clinical trial data and to verify the data that will be used for analysis set classification. If required, consequences for the statistical analysis will be discussed and documented. A meeting to determine analysis set classifications may also be held prior to database hard lock.

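### Protocol 1.4 gives the sponsor's Medical Monitor an unlimited duty to review unblinded trial data, which conflicts with the blinding rules in 4.4 and is not reconciled anywhere

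*Protocol*

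**What the plan says.** The last part of Protocol 1.4 (Risk-Benefit Assessment) assigns a responsibility: "Medical monitor will be responsible for reviewing the unblinded data from the trial to ensure the safety of the subjects". It does not say which data, when, on what trigger, or with what separation from other duties.

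The blinding section reads differently:

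- **4.4.1:** under the double-blind design, "neither the investigator, sponsor's study management team, clinical staff, nor the subject will know which agent is being administered". SAP 7.4 repeats this list when it defines the double-blind period and adds no exception.
- **4.4.3:** the IRT holds the randomization list. A subject who stops treatment with confirmed radiographic progression may be unblinded if the investigator needs the information to choose the next therapy. The Medical Monitor's part is to be told first: "Prior to unblinding in this scenario, the investigator must contact the Astellas Medical Monitor".
- **4.4.4:** "The treatment code for each randomized subject will be provided by the IRT in the event of a medical emergency". Only the investigator or subinvestigators may request these codes. The section adds that, short of a medical emergency that requires it, no subject and no other member of the study personnel is to learn any subject's treatment.
- **4.4.5:** the sponsor may break the code for SUSARs, "in order to determine if the individual case or a group of cases requires expedited regulatory reporting". The codes go to limited staff, for reporting. The Medical Monitor is not named.

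Protocol 7.8 and 10.1 describe one review of aggregate data by treatment assignment: the interim analysis, run by an independent data analysis group (DAC) and reviewed by the IDMC. The SAP introduction describes the pre-lock review as blinded: "Prior to database hard lock, a final blinded review of data and TLFs meeting will be held". It does not say who attends.

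**The concern.** The Medical Monitor belongs to the sponsor. Protocol 4.4.3 and 4.4.4 use the sponsor's name in the title, and 5.5.5 says "The investigator may contact the sponsor's Medical Monitor/Study Physician for any other problem related to the safety, welfare or rights of the subject". The role also has a part in the handling of individual subjects while treatment is double-blind. On dose changes, Protocol 5.1.2 states: "If restarted at a lower dose or if interrupted for > 2 weeks, the Medical Monitor must be consulted". Under Protocol 6.1, the Medical Monitor's opinion that a subject is noncompliant is by itself a ground for stopping study drug.

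If 1.4 were followed as written, the person giving those opinions would know the assignments, and neither document describes a separation. Advice on restarts, or findings of noncompliance, could then differ by arm. At stake is the integrity of the blind as the trial's own text defines it and, through discontinuation dates, some of the analyses.

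**Working it through.** No formula applies, because the point depends on no alpha, power, event count or sample size. The check sets the provisions on blinding, code breaking, by-assignment review and Medical Monitor duties side by side.

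1. **Does any provision in 4.4 give the access that 1.4 presupposes?** No. There are three routes to a code: after radiographic progression (4.4.3), in a medical emergency (4.4.4), and for a SUSAR case or group of cases (4.4.5). Each is tied to cases. In the first two the Medical Monitor is a contact before the code is broken, not a holder of codes. In the third the holders are limited staff with a reporting task.

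2. **Does any provision exclude it?** Yes. The restriction in 4.4.4 covers other study personnel in general, so the conflict does not rest only on placing the Medical Monitor within the study management team named in 4.4.1. Sections 4.4.3 and 4.4.5 add their own exceptions, but neither amounts to standing review of the trial's data.

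3. **Is aggregate review by assignment allocated elsewhere?** Yes, to the DAC and the IDMC at the interim (Protocol 7.8 and 10.1; SAP 7.11). The Medical Monitor is not mentioned there.

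4. **Does other text reconcile the two?** No. SAP 7.4 repeats 4.4.1 without an exception, and 1.4 does not refer to 4.4, the IDMC charter or the Interim Analysis Plan.

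5. **Which results could be touched if 1.4 were followed?**
   - *Primary TTPP:* little. PSA comes from the central laboratory and progression follows a fixed numerical rule with confirmation (SAP 6.1.1.1). Under SAP 7.4.1, stopping study drug does not by itself censor a subject; the discontinuation rule there refers to leaving the entire study.
   - *Analyses tied to the date of stopping:* more. These are the two treatment-discontinuation sensitivity analyses (SAP 6.1.1.2 and Appendix 1) and the 24-week death window in rPFS (SAP 6.1.2.1).
   - *Weight of those results:* SAP 7.1 says p-values for endpoints other than the primary are descriptive, which covers rPFS. The sensitivity analyses support the primary test and are not separate confirmatory claims.

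6. **Can the effect be sized?** No. The documents do not give the number of restarts on which the Medical Monitor was consulted, or the number of noncompliance findings by that role.

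**The case against.** The strongest reply is that this is one ambiguous sentence in a background section, not a working instruction. Section 4.4.1 does not name the Medical Monitor, and 4.4.5 shows that some sponsor staff may hold codes, so a sponsor role is not necessarily a blinded one. Unblinded may be a slip for blinded. It may mean subjects already unblinded under 4.4.3 to 4.4.5, or those on open-label enzalutamide before study-wide unblinding, where the Medical Monitor also has a role (12.10.4 and 12.10.6). It may refer to the aggregate comparison of listed serious events foreseen in Protocol 12.6, which needs assignments. The charter and Interim Analysis Plan are not among the documents and may describe a separation. In practice the IRT holds the list and emergency requests are restricted, so 1.4 supplies no route to the codes. On restarts, the Medical Monitor is consulted and does not decide.

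Much of this stands. It limits the consequence, and it means that including the Medical Monitor under 4.4.1 is an inference. It does not remove the conflict. The restriction in 4.4.4 is general, 12.6 does not give its comparison to the Medical Monitor, and no text says which benign reading is meant.

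A reader might go further and infer that the blind was broken, or that the primary result is biased. The documents support neither. Nothing shows that any Medical Monitor saw assignments, and the primary endpoint is largely insulated for the reasons given above.

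**Conclusion.** The point holds as a minor one. Section 1.4 gives a sponsor role a duty that the trial's own blinding rules do not permit, and neither document reconciles them. That textual conflict is clear. The consequence is conditional: it arises only if 1.4 was meant and followed literally, and only through consultation on restarts and opinions on noncompliance. No size can be given. Any effect on primary TTPP would be limited, and the more exposed results are sensitivity analyses and a secondary endpoint read descriptively.

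The conclusion assumes that the Medical Monitor counts as study personnel in the sense of 4.4.4, which the sponsor affiliation and the subject-level duties support. A charter that described a separation would reduce the practical concern, but 1.4 would still need correcting.

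**What to change.** - **Protocol 1.4:** say that the Medical Monitor reviews blinded safety data, without treatment assignments, except for subjects already unblinded under 4.4.3 to 4.4.5 or treated in the open-label phase.
- **Protocol 4.4.1:** list the Medical Monitor and designee among the blinded parties, subject to the same exceptions.
- **Clinical study report:** state whether any Medical Monitor had treatment assignments before study-wide unblinding outside those exceptions. This is useful even if conduct is complete, because it tells readers whether the blind held as 4.4 describes.

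The cost is one sentence, one added role and one disclosure, with the protocol changes going through the amendment process in 12.1.3. The downside is that the sponsor's monitor has no arm-level access before the interim. Sponsor monitoring of the frequency of listed serious events (5.5.7) and SUSAR code breaks (4.4.5) would continue unchanged.

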## **2 STUDY OBJECTIVE(S), DESIGN, AND ENDPOINTS**

### **2.1 Study Objectives**

The objective of this phase 3 study is to evaluate the efficacy and safety of enzalutamide plus ADT versus placebo plus ADT in Chinese subjects with mHSPC.

#### **2.1.1 Primary Objective**

- To determine the benefit of enzalutamide plus ADT as compared to placebo plus ADT as assessed by time to prostate-specific antigen (PSA) progression based on central laboratory test

#### **2.1.2 Secondary Objectives**

- To determine the benefit of enzalutamide plus ADT as compared to placebo plus ADT as assessed by radiographic progression-free survival (rPFS)
- To determine the benefit of enzalutamide plus ADT as compared to placebo plus ADT as assessed by time to first Symptomatic Skeletal Event (SSE)
- To determine the benefit of enzalutamide plus ADT as compared to placebo plus ADT as assessed by time to castration resistance
- To determine the benefit of enzalutamide plus ADT as compared to placebo plus ADT as assessed by PSA response ( $\geq 50\%$ )
- To determine the benefit of enzalutamide plus ADT as compared to placebo plus ADT as assessed by PSA response ( $\geq 90\%$ )

- CONFIDENTIAL -

- To determine the benefit of enzalutamide plus ADT as compared to placebo plus ADT as assessed by time to start of new antineoplastic therapy
- To determine the benefit of enzalutamide plus ADT as compared to placebo plus ADT as assessed by PSA undetectable rate (< 0.2 ng/mL)
- To determine the benefit of enzalutamide plus ADT as compared to placebo plus ADT as assessed by objective response rate (ORR)

